5.2. General Methods

Unless otherwise explicitly stated, descriptive statistics for continuous variables are n, mean, median, standard deviation, minimum, and maximum. Descriptive statistics for categorical variables are the percentage (%) and the numerator (n) and the denominator (N) used in the percentage calculation.

5.2.1. Analyses for Binary Data

For immunogenicity results, the exact 2-sided 95% CIs (Clopper-Pearson CIs) will be provided for the proportions of subjects achieving an IgG concentration $\geq 0.35 \ \mu g/mL$, and the proportion of subjects with pneumococcal OPA titer \geq LLOQ for each vaccine group at defined sampling time point in each cohort, as defined in Section 3.2.1.

The exact CIs (Clopper-Pearson) for the various proportions of individual groups will be computed using the F distribution. If r is the number of responses and n is the number of subjects, then it follows that p=r/n is the estimate of the proportion of responses. An exact 95% CI can be computed by solving the following 2 equations. For the lower limit P_L ,

$$p_L = \frac{rF_L}{(rF_L + (n-r+1))}$$

and for the upper limit P_U ,

$$p_U = \frac{(r+1)F_U}{(n-r) + (r+1)F_U}$$

where F_L is the quantile from the F distribution for α =0.025, with numerator degrees of freedom equal to 2r and denominator degrees of freedom equal to 2(n–r+1). F_U is the quantile from the F distribution for α =0.975, with numerator degrees of freedom equal to 2(r+1) and denominator degrees of freedom equal to 2(n–r). When r equals 0, F_L should be set equal to 1.0 so P_L equals 0. When r equals n, F_U should be set equal to 1.0 so P_U equals 1.0.

The CI using the F distribution is described in Collett (1991) and implemented in SAS PROC FREQ.

The proportion differences for each serotype in 13vPnC between 1 month after the last vaccination of each cohort (Cohort 2, Cohort 3, Cohort 4) and 1 month after last vaccination of infant series of Cohort 1; and proportion differences between 13vPnC and Hib vaccine in Cohort 2, Cohort 3, Cohort 4 will be provided along with associated exact 2-sided 95% CIs by Chan and Zhang's method (1999).

Similarly, for the safety results in infants and children 7 months to <6 years of age (Cohorts 2, 3, and 4), the exact 2-sided 95% CIs will be provided by vaccine group in each Cohort for all primary safety endpoints, proportions of subjects reporting local reactions, systemic events, and AEs (including AEs occurring within the first 30 minutes after each vaccination).

For tier 1 AEs, an unconditional exact method for deriving the 95% CI for the risk difference and p-value proposed by Chan and Zhang (1999) will be used to compare 13vPnC with Hib vaccine.

For tier 2 AEs, the Miettinen and Nurminen method will be used to derive the 95% CI for the risk difference between 13vPnC and Hib vaccine.

5.2.2. Analyses for Continuous Data

For each of the 13 serotypes contained in 13vPnC, GMCs will be calculated at 1 month after the last vaccination for Cohort 2, Cohort 3, Cohort 4, and 1 month after infant series for Cohort 1, along with 2-sided 95% CIs on the GMCs, which will be constructed by back transformation of the CIs for the mean of the logarithmically transformed IgG computed using Student's t distribution. In addition, the 2-sided 95% CI on the geometric mean ratios (GMRs) (the GMC of 13vPnC at 1 month after the last vaccination of Cohort 2, Cohort 3, Cohort 4 to the GMC of 13vPnC at 1 month after the last vaccination of infant series of Cohort 1, and the GMT of 13vPnC at 1 month after the last vaccination of Cohort 2, Cohort 3, Cohort 4 to the GMT of 13vPnC at 1 month after the last vaccination of Cohort 2, Cohort 3, Cohort 4 to the GMT of 13vPnC at 1 month after the last vaccination of Cohort 2, Cohort 3, Cohort 4 to the GMT of 13vPnC at 1 month after the last vaccination of the series of Cohort 1) for all 13 serotypes will be also provided and those 95% CIs will be calculated using Student's t distribution for the mean difference of the measures on the natural log (ln) scale. GMRs with IgG and OPA assessments from blood samples taken before vaccination between Cohort 2, 3, or 4 and Cohort 1 will also be provided with associated 2-sided 95% CIs.

Within each cohort in the age of 7 months to < 6 years (Cohort 2, Cohort 3, Cohort 4), the GMRs (IgG GMC of 13vPnC/GMC of Hib vaccine and OPA GMT of 13vPnC/GMT of Hib vaccine) and associated 2-sided 95% CIs on GMRs produced by a similar approach as described above will be provided.

The GMCs and GMTs at each blood draw time point in each cohort will be provided by vaccine group. The geometric mean fold rises (GMFRs) in IgG and OPA from before vaccination to after vaccination at all postbaseline blood sampling time points thought 1 month after infant series for Cohort 1, and all postbaseline blood sampling time points for Cohort 2, 3 and 4, will be summarized with 2-sided 95% CIs, also computed using the logarithmically transformed assay results. In addition, the GMFRs in IgG and OPA from before toddler dose to after toddler dose at all post–toddler dose blood sampling time points for Cohort 1 will be summarized with corresponding 2-sided 95% CIs. The ratios of GMFRs in IgG and OPA (the GMFR of 13vPnC at 1 month after the last vaccination of Cohort 2, Cohort 3, Cohort 4 to the GMFR of 13vPnC at 1 month after the last vaccination of infant series of Cohort 1) and corresponding 2-sided, 95% CIs will be calculated. The CIs will be computed by back transformation of the CIs using the Student t distribution for the mean difference of the measures on the logarithmic scale (IgG/OPA difference between 1 month after the last vaccination.

GMRs between GMCs/GMTs of Cohort 1 persistency blood samples and GMCs/GMTs of Cohort 2, 3, 4 prevaccination blood samples and associated 2-sided 95% CIs will also be provided.

Reverse cumulative distribution curves (RCDCs) will be presented graphically by vaccine group separately for each serotype-specific pneumococcal IgG concentration and OPA titer at each blood draw time point in each cohort.

The persistence of antibody response for cohort 1 (post-toddler dose) will be displayed graphically for both IgG concentrations and OPA titers.

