3. STUDY DESIGN

3.1. Description

- This is a phase 3 randomized, open-label study to evaluate the safety, tolerability, and immunogenicity of 13vPnC of infants and young children who are naïve to pneumococcal vaccination.
- Subjects will be stratified into 4 cohorts defined by their age at consent:
 - Cohort 1: Subjects 6 weeks (42 days) to 2 months (56 days) of age;
 - Cohort 2: Subjects 7 months (210 days) to <12 months (<365 days) of age;
 - Cohort 3: Subjects ≥ 1 year to ≤ 2 years of age;
 - Cohort 4: Subjects ≥ 2 years to < 6 years of age.
- Subjects in Cohort 1 will all receive 13vPnC at 2, 4, 6 and 12 to 15 months of age. See Table 5 below.
- Subjects in Cohorts 2, 3, and 4 will be randomized into 2 groups in a 2:1 ratio to receive 13vPnC or comparator (Hib vaccine) according to age-appropriate schedules. See Table 5 below.

		Age at first vaccination	Age at second vaccination	Age at third vaccination	Age at fourth vaccination
Cohort 1	13vPnC	42 to 56	42 to 70 Days	42 to 70 Days	365 to 455
		Days of Age	After Visit 1	After Visit 2	Days
					of Age
Cohort 2	13vPnC	7 to <12	At Least 28 Days	365 Days to <450 Days	
	or	Months of Age	After Visit 1	of Age and at Least 56	
_	Hib			Days After Visit 2 ^a	
Cohort 3	13vPnC	≥ 1 to ≤ 2	At Least 56 Days		
	or	Years of Age	After Visit 1 ^b		
	Hib				
Cohort 4	13vPnC	≥ 2 to ≤ 6		_	
	or	Years of Age			
	Hib	_			

Table 5.Age at Vaccination

a. Subjects in Cohort 2 randomized to Hib vaccine will not receive a vaccination at Visit 3. These subjects may receive a third dose of Hib vaccine according to local practice or national recommendations, at the discretion of the investigator.

b. Subjects in Cohort 3 randomized to Hib vaccine will not receive a vaccination at Visit 2.

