7.5.1. IgG Assessments

Serum concentrations of anticapsular IgG for each of the 13 pneumococcal serotypes (1, 3, 4, 5, 6A, 6B, 7F, 9V, 14, 18C, 19A, 19F, and 23F) will be determined in all subjects for each blood sample collected and expressed as micrograms per milliliter (μ g/mL). The assay will employ 2 adsorbents: a C polysaccharide-containing cell wall extract plus serotype 22F capsular polysaccharide.

Cohort 1: Serotype-specific IgG concentrations to the 13 pneumococcal serotypes (1, 3, 4, 5, 6A, 6B, 7F, 9V, 14, 18C, 19A, 19F, and 23F) will be determined in all subjects from the blood samples taken before vaccination, 1 month after the infant series, before the toddler dose, 1 month after the toddler dose and at yearly intervals for 4 years after the last vaccination.

Cohorts 2, 3, 4: Serotype-specific IgG concentrations to the 13 pneumococcal serotypes (1, 3, 4, 5, 6A, 6B, 7F, 9V, 14, 18C, 19A, 19F, and 23F) will be determined in all subjects from the blood samples taken before vaccination and after vaccination in each of the 3 cohorts (See schedule of activities for timing of blood samples.)

Additional 280 subjects (177 subjects of Cohort 2, 73 subjects of Cohort 3, and 30 subjects of Cohort 4): Serum concentrations of anticapsular IgG for each of the 13 pneumococcal serotypes (1, 3, 4, 5, 6A, 6B, 7F, 9V, 14, 18C, 19A, 19F, and 23F) will be determined in all subjects from the blood samples taken before vaccination and after vaccination in the additional subjects.

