7.5.2. OPA Assessments

Serum levels of OPA for each of the 13 pneumococcal serotypes (1, 3, 4, 5, 6A, 6B, 7F, 9V, 14, 18C, 19A, 19F, and 23F) will be determined in all selected subjects for each blood sample collected and expressed as titers.

Cohort 1: Serotype-specific OPA titers to the 13 pneumococcal serotypes (1, 3, 4, 5, 6A, 6B, 7F, 9V, 14, 18C, 19A, 19F, and 23F) will be determined in a randomly selected subset of approximately 50 subjects from the blood samples taken before vaccination, 1 month after the infant series, before the toddler dose, 1 month after the toddler dose and at yearly intervals for 4 years after the last vaccination.

Cohorts 2, 3, 4: Serotype-specific OPA titers to the 13 pneumococcal serotypes (1, 3, 4, 5, 6A, 6B, 7F, 9V, 14, 18C, 19A, 19F, and 23F) will be determined in a randomly selected subset of approximately 50 subjects receiving 13vPnC and approximately 25 subjects receiving Hib vaccine from the blood samples taken before vaccination and 1 month after the last vaccination in each of the 3 cohorts.

Additional 280 subjects (177 subjects of Cohort 2, 73 subjects of Cohort 3, and 30 subjects of Cohort 4): Serotype-specific OPA titers to the 13 pneumococcal serotypes (1, 3, 4, 5, 6A, 6B, 7F, 9V, 14, 18C, 19A, 19F, and 23F) will be determined in a randomly selected subset.

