9.5. Sample Size Calculation

The type I error for all comparisons between each cohort in the age of 7 months to < 6 years and Cohort 1 (infant) is 5% (or 2.5%, 1-sided test of non-inferiority). As all comparisons between children with age of 7 months to < 6 year and infants are independent of each other, the type I error is not adjusted.

Sample size estimations are based upon GMCs in all Cohorts and data from studies in China (B1841008, and B1851015). The sample size/power estimates for non-inferiority of each Cohort in the age of 7 months to < 6 years relative to the Cohort 1 are evaluated based on following assumptions:

- 1. 2-sided type I error of 5%,
- 2. 2-fold non-inferiority criterion for GMC,
- 3. differences in true GMCs for 7 common serotypes (4, 6B, 9V, 14, 18C, 19F, 23F) between each Cohort in the age of 7 months to < 6 years and the Cohort 1 (infant) are the same as the data observed in study B1841008,
- 4. differences in true GMCs for 6 additional serotypes (1,3,5, 6A, 7F, 19A) between each cohort in the age of 7 months to < 6 years and Cohort 1 are zero and GMCs of these 6 additional serotype for Cohort 1 are the same as 1 month after infant series in Group 3 from study B1851015.

This assumption (d) may be conservative as actually better GMCs in the children of 7 months to <6 years for these 6 additional serotypes were observed when compared GMCs between 1 month after last dose in the age of 7 months to <6 years and 1 month after infant series in the studies performed in Poland (6096A1-3000 and 6096A1-3002).

The sample size estimations for non-inferiority of 13vPnC in the Cohort 2 (age 7 months to < 12 months) relative to 13vPnC in the Cohort 1 are presented in Table 12. Non-inferiority assumptions are as stated above, the 7vPnC data for Cohort 1 were based on GMC results of 1 month after infant series in Group 1 of study B1841008, and 7vPnC data for Cohort 2 were based on GMC results of 1 month after last vaccination of Group 2 in study B1841008. With a 2:1 randomization ratio (13vPnC : Hib vaccine) in the Cohort 2, a total of 150 evaluable subjects will provide 100 evaluable subjects with 13vPnC and therefore provide more than 90% power to declare non-inferiority relative to Cohort 1 across all 13 serotypes. With about 15% of randomized subjects nonevaluable in the Cohort 2, the total number of subjects to be randomized in Cohort 2 will be 177.

	Co	hort 1(13vP	nC)	Co	hort 2(13vP	nC)	Differenc	Common	Power N= 200 (100:100)

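### The randomised 13vPnC/Hib GMRs are valid as planned, but give up precision by not adjusting for the Visit 1 value already collected

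*SAP*

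**What the plan says.** SAP 5.2.2 plans, within each of Cohorts 2, 3 and 4, "the GMRs (IgG GMC of 13vPnC/GMC of Hib vaccine and OPA GMT of 13vPnC/GMT of Hib vaccine"). On the precision of these ratios, the section states: "associated 2-sided 95% CIs on GMRs produced by a similar approach as described above will be provided". The approach above it in that section is an interval "calculated using Student's t distribution for the mean difference of the measures on the natural log (ln) scale". Protocol 9.2.2 says the same. Neither document names a covariate for this contrast.

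The baseline is available. Under Protocol 7.5.1, IgG "will be determined in all subjects from the blood samples taken before vaccination and after vaccination in each of the 3 cohorts". Under Protocol 7.5.2, OPA is measured before and after vaccination in a "randomly selected subset of approximately 50 subjects receiving 13vPnC and approximately 25 subjects receiving Hib vaccine" in each of these cohorts. The arms are randomised: children in Cohorts 2 to 4 "will be randomized into 2 groups in a 2:1 ratio to receive 13vPnC or comparator (Hib vaccine").

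The plan does use Visit 1 in other ways. SAP 6.2.1 tabulates the 13vPnC/Hib GMR at Visit 1 and the fold rise by vaccine group. SAP 5.2.2 adds a ratio of fold rises, but only against Cohort 1. None of these adjusts the post-vaccination 13vPnC/Hib GMR.

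**The concern.** The comparison with Hib serves a stated secondary objective, and it sets randomised groups side by side, which the comparisons with Cohort 1 do not. In a randomised contrast, a baseline measurement of the same quantity is the obvious covariate. Hib recipients get no pneumococcal antigen from the study vaccine, so their later value may well follow their Visit 1 value. If pre and post values are correlated within arms, an unadjusted interval is wider than the collected data require. What is at stake is the width of 13 GMR intervals per cohort and assay. The validity of the comparison is not in question.

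**Working it through.** **Plan's own figures.** No power or precision is stated for the 13vPnC/Hib GMRs. The figures that fix the group sizes do reproduce.
- Protocol 9.5: "a total of 150 evaluable subjects will provide 100 evaluable subjects with 13vPnC", which leaves 150 − 100 = 50 Hib recipients. "With about 15% of randomized subjects nonevaluable in the Cohort 2" gives 150 / 0.85 = 176.5, so 177.
- Power against Cohort 1: noncentral t, one-sided 0.025, 100 per group, noncentrality (ln 2 + difference) / (SD × √(2/100)), multiplied over 13 serotypes. This gives 0.9899, 0.9946 and 0.8868, against the stated 0.990, 0.995 and 0.887. These powers concern a different comparison.

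**Inputs for this contrast.**
- Group sizes: IgG 100:50 evaluable; OPA about 50:25.
- ln SD: 0.9 in both arms, assumed. The common SDs in Tables 12 to 14 run from 0.640 to 1.294, but they describe IgG after pneumococcal vaccination, not Hib recipients or OPA.
- Within-arm pre/post correlation r: not in the documents; assumed range 0.1 to 0.7.

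**Unadjusted interval.** SE = SD × √(1/n1 + 1/n0).
- IgG: 0.9 × √(1/100 + 1/50) = 0.156. The 95% limits multiply and divide the GMR by 1.361.
- OPA: 0.9 × √(1/50 + 1/25) = 0.220, factor 1.552.

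**Adjusted interval, same r in both arms.** The SE is multiplied by √(1 − r²).

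| r | √(1 − r²) | Log-scale narrowing | IgG factor | OPA factor |
|---|---|---|---|---|
| 0 (unadjusted) | 1 | none | 1.361 | 1.552 |
| 0.1 | 0.995 | 0.5% | 1.359 | 1.548 |
| 0.3 | 0.954 | 5% | 1.342 | 1.521 |
| 0.5 | 0.866 | 13% | 1.306 | 1.463 |
| 0.7 | 0.714 | 29% | 1.246 | 1.369 |

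For IgG at r = 0.5, the factor goes from 1.228 to 1.195 at SD 0.6, and from 1.560 to 1.470 at SD 1.3.

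**Different correlations by arm.** Take correlation 0 in 13vPnC and 0.5 in Hib, unit SDs, 100:50. The unadjusted variance is 1/100 + 1/50 = 0.0300.
- Common slope: b = (100 × 0 + 50 × 0.5)/150 = 0.167. Variance = (1 + b²)/100 + (1 − 2 × 0.5b + b²)/50 = 0.0275. SE ratio √(0.0275/0.0300) = 0.957.
- Separate slopes, Visit 1 centred at the cohort mean: effective b = (50 × 0 + 100 × 0.5)/150 = 0.333. The same formula gives 0.0267. SE ratio 0.943.

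So the gain is about 4% with one slope and about 6% with two. Other pairs (13vPnC, Hib): (0.1, 0.7) gives 0.889 and 0.866; (0.3, 0.8) gives 0.792 and 0.774. A pair such as (−0.3, 0.3), which is hard to believe, removes the common-slope gain (1.015).

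**Ratio of fold rises as a substitute.** With equal SDs and common r, its SE relative to the unadjusted GMR is √(2(1 − r)): 1.18 at r = 0.3 and 1.00 at r = 0.5. It is not equivalent to adjustment and can be worse than none.

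**Time between samples (schedule of activities).** Cohort 4: 28 to 42 days. Cohort 3: at least 56 + 28 = 84 days. Cohort 2: at least 28 + 56 + 28 = 112 days. Tracking is most plausible in Cohort 4.

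**The case against.** The strongest reply is that nothing turns on this. Protocol 9.2.2 makes the secondary immunogenicity endpoints descriptive, and SAP 5.1 gives nominal intervals without a decision rule. The contrast sets a vaccine containing the antigen against one that does not. A change of factor from 1.361 to 1.342 or 1.306 is unlikely to alter anyone's reading. That stands, and it makes this an optional improvement.

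Several stronger readings are tempting, and the documents do not support them:
- A reader might infer that chance baseline imbalance distorts the planned GMR. It does not bias it. Allocation is randomised, and such imbalance is part of the sampling error that the t interval already covers. Counting it as well as the wider interval counts one variance twice.
- A reader might infer that the plan ignores baseline. The Visit 1 GMR and the fold rises by arm are tabulated, so an imbalance would be visible, though not adjusted for.
- A reader might infer that every child has both baselines. That holds for planned IgG; OPA is planned for a subset only.
- A reader might infer that OPA gains most. The factor √(1 − r²) does not depend on sample size, so the relative gain is no larger there. SAP 5.3.1 assigns half the LLOQ of 8 to every lower OPA titre. If many Visit 1 titres fall there (the share is not given), the covariate carries little information.
- A reader might infer that these GMRs are the only randomised immunogenicity contrasts. SAP 5.2.1 also plans 13vPnC/Hib proportion differences.

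Timing is a further fair objection. SAP section 2 says that the analyses had been performed for the primary report. Adjustment introduced now is decided after results were available in an open-label study, so it cannot replace the planned estimate.

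**Conclusion.** The point holds as a modest and inexpensive gain in precision. The planned estimate is valid; it leaves unused a covariate that the trial already collects. With a common correlation of 0.1, 0.3, 0.5 or 0.7, the log-scale interval would be about 0.5%, 5%, 13% or 29% narrower. The gain is about 4% to 6% if correlation exists only in Hib recipients (0 versus 0.5). It would be smaller still with many Visit 1 values below the LLOQ or with the longer sampling gaps of Cohorts 2 and 3. The percentages rest on assumed correlations and on equal SDs across arms and visits. The factors such as 1.361 also rest on the assumed ln SD of 0.9 and on 100:50 or 50:25 evaluable children. The non-inferiority comparisons with Cohort 1 are not affected.

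**What to change.** In SAP 5.2.2 and 6.2.1, add for each serotype and cohort a regression of ln(post-vaccination value) on arm, ln(Visit 1 value) centred at the cohort mean, and their product, with robust variance. Back-transform the arm coefficient to a GMR with a 95% CI. Separate slopes suit this contrast because the reason for expecting correlation applies mainly to the Hib arm and allocation is 2:1. Keep the unadjusted GMR beside it.

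One detail for the programmer: the usual robust variance treats the cohort mean as fixed. When slopes differ, add (slope difference)² × Var(ln Visit 1)/n. In the 0 versus 0.5 example this is 0.25/150 = 0.0017 of the 0.0267, and the 6% gain above already counts it.

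Write the model down before the repeat analysis with the additional 280 subjects, and label the adjusted line there as supplementary.

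The cost is SAP wording and one model per serotype, cohort and assay. No new data are needed. Protocol section 9 lets the SAP modify the analyses and asks for an amendment only for major changes to the primary endpoints. Children without a Visit 1 result drop from the adjusted line only, which SAP 5.3 already allows. No decision rule changes.

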5.3. Methods to Manage Missing Data

In general, nonmissing values will not be excluded from the analysis. However, certain statistical procedures that compare 2 or more variables, or values at more than 1 time point, for the same subject require all values to be available. In such cases, nonmissing values will be dropped to the extent necessary to perform the procedure.

5.3.1. Immunogenicity Data

Immunogenicity data collected for this study are the results of immunologic assays performed by the National Institutes for Food and Drug Control (NIFDC) on the blood samples collected.

The LLOQ in micrograms per mL (μ g/mL) for each serotype is shown in Table 10.

Serotype	LLOQ
1	0.02
3	0.03
4	0.02
5	0.03
6A	0.03
6B	0.03
7F	0.04
9V	0.02
14	0.04
18C	0.02
19A	0.02
19F	0.03
23F	0.03

Table 10. The LLOQ in Micrograms per mL from NIFDC

Antibody concentrations above LLOQ are considered accurate and their quantitated values will be reported. The Limit of detection (LOD) was established as 50% of the LLOQ. Values below the LLOQ or denoted Below Limit of Quantification (BLQ) will be set to $0.5 \times \text{LOD}$ for analysis.

The NIFDC's OPA LLOQ in titers for all serotypes was set as 8. For the results of antibody titers that are below the LLOQ, or denoted as BLQ, $0.5 \times LLOQ$ will be assigned for analysis.

No other missing assay data will be imputed in the analyses. All immunogenicity analyses will be performed after the imputation of the antibody concentrations or antibody titers that are below the LLOQ.

For each serotype's antibody concentrations or antibody titers, the number of subjects with missing values at each blood sampling point will be provided.

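### IgG results below the LLOQ are set to a quarter of the LLOQ, unlike OPA and without a stated reason; fold rises could be inflated if such results are common, and no check is planned

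*SAP*

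**What the plan says.** SAP 5.3.1 gives the IgG LLOQ by serotype in Table 10 (0.02, 0.03 or 0.04 µg/mL) and defines the detection limit from it: "The Limit of detection (LOD) was established as 50% of the LLOQ". For IgG it continues: "Values below the LLOQ or denoted Below Limit of Quantification (BLQ) will be set to" 0.5 × LOD.

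The next paragraph of the section treats OPA differently. "The NIFDC's OPA LLOQ in titers for all serotypes was set as 8", and "For the results of antibody titers that are below the LLOQ, or denoted as BLQ", the assigned value is 0.5 × LLOQ.

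The substitution has a wide reach: "All immunogenicity analyses will be performed after the imputation of the antibody concentrations or antibody titers that are below the LLOQ". Under SAP 5.2.2 that covers:
- pre-vaccination GMRs against Cohort 1;
- 13vPnC/Hib GMRs;
- fold rises ("The geometric mean fold rises (GMFRs) in IgG and OPA from before vaccination to after vaccination");
- "The ratios of GMFRs in IgG and OPA" between Cohorts 2 to 4 and Cohort 1;
- GMRs of Cohort 1 persistence samples against pre-vaccination samples of the older cohorts.

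SAP 6.3.1.4 plans a table counting subjects below the LLOQ. No section gives a reason for the IgG value, a second substitution rule or a censored-data analysis.

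**The concern.** A sample between the LOD and the LLOQ is detectable by the SAP's own definition, yet it is scored at half the LOD. Values that low are plausible for some censored samples, but not for most of them when only a modest share is censored.

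The error would not cancel in comparisons between groups with different censored shares. Pre-vaccination and Hib-arm samples are where results below the LLOQ could occur; post-13vPnC samples should almost never fall there. If the share is low to moderate, the baseline and Hib GMCs come out too low, and fold rises and 13vPnC/Hib GMRs come out too high, in the vaccine's favour. The SAP version history shows that the cross-cohort fold-rise comparison was added in version 2, in the same entry as analyses for the regulator, so these outputs will be read. The difference from OPA also means that IgG and OPA fold rises for the same subjects rest on different conventions.

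**Working it through.** **1. The rule.** 0.5 × LOD = 0.5 × 0.5 × LLOQ = 0.25 × LLOQ.

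| Serotypes (SAP Table 10) | LLOQ | LOD | Assigned | Half LLOQ |
|---|---|---|---|---|
| 1, 4, 9V, 18C, 19A | 0.02 | 0.010 | 0.005 | 0.010 |
| 3, 5, 6A, 6B, 19F, 23F | 0.03 | 0.015 | 0.0075 | 0.015 |
| 7F, 14 | 0.04 | 0.020 | 0.010 | 0.020 |

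OPA: 0.5 × 8 = 4.

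**2. One rule against the other.** Let p be the share of samples below the LLOQ. The quarter rule multiplies a GMC by 0.5^p relative to half-LLOQ. It multiplies a fold rise from that baseline by 2^p if no post-dose values are censored: 1.035 at 5%, 1.072 at 10%, 1.149 at 20%, 1.231 at 30%, 1.414 at 50%, never above 2.

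**3. Each rule against uncensored values.** Assume ln concentrations are normal with SD s, and let a = Φ⁻¹(p). The true geometric mean of the censored samples, as a fraction of the LLOQ, is r = exp{s(−φ(a)/p − a)}. A rule that assigns c × LLOQ gives GMC/true = (c/r)^p, and the fold rise is off by the reciprocal.

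Example with s = 1.0 and p = 20%: a = −0.842 and φ(a) = 0.280, so the exponent is −1.400 + 0.842 = −0.558 and r = 0.572. Then (0.25/0.572)^0.2 = 0.847, and the fold rise is multiplied by 1/0.847 = 1.18.

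| Share below LLOQ (s = 1.0) | r | GMC/true, quarter | Fold-rise error | GMC/true, half | Fold-rise error |
|---|---|---|---|---|---|
| 10% | 0.623 | 0.913 | +10% | 0.978 | +2% |
| 20% | 0.572 | 0.847 | +18% | 0.973 | +3% |
| 30% | 0.530 | 0.798 | +25% | 0.983 | +2% |
| 50% | 0.450 | 0.745 | +34% | 1.054 | −5% |

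The same factors apply to a 13vPnC/Hib GMR after vaccination when only the Hib arm has censored values.

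**4. Other spreads.** The ln SDs in protocol Tables 12 to 14 run from 0.596 to 1.382. They are post-vaccination values, used here only as a guide. At a 30% share, GMC/true for quarter and half is 0.739 and 0.910 at SD 0.596, 0.845 and 1.040 at SD 1.3, and 0.858 and 1.057 at SD 1.382. Half-LLOQ is closer each time. At higher shares with wide spread this stops: at SD 1.3 the pair is 0.840 and 1.188 at 50%, 0.960 and 1.559 at 70%, and 1.139 and 1.983 at 80%.

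**5. Detectable samples scored as undetectable.** The fraction of censored samples that lie above the LOD is 1 − Φ(a − ln 2/s)/p. With s = 1.0 it is 76, 69 and 51% at shares of 10, 20 and 50%. With s = 1.3 it is 58% at a 20% share and 41% at 50%.

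**6. Ratio of fold rises to Cohort 1.** Relative to half-LLOQ, the quarter rule multiplies it by 2^(p_older − p_Cohort 1). With 5% in the older cohort and 30% in Cohort 1 the factor is 2^(−0.25) = 0.84; reversed, it is 1.19.

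**7. Primary endpoint.** The highest post-dose share implied by Tables 12 to 14 is for 19F in Cohort 1 (GMC 3.60, ln SD 1.275, LLOQ 0.03): Φ((ln 0.03 − 1.281)/1.275) = Φ(−3.755) = 0.009%. The effect on that GMC is at most a factor 2^0.00009 = 1.00006. The 0.35 µg/mL threshold is 8.75 to 17.5 times the LLOQs, so a censored sample counts as below it under either rule.

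**The case against.** The best defence is that no one can tell from the documents whether the rule does any harm. No share below the LLOQ is given, and with LLOQs so far under 0.35 µg/mL it may be small; at 5% the two rules differ by only 3.5%. The rule is explicit and reproducible, two assays need not share a convention, and the count of censored results and the reverse cumulative distribution curves will be reported. The affected endpoints are secondary and descriptive. SAP section 2 also says the planned analyses were already performed for the primary study report and will be repeated with the 280 additional subjects. Replacing the rule now would be a change made after results in an open-label study, and would make the two reports hard to compare.

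Most of this stands. It limits the point to a conditional one and rules out swapping the rule. It does not explain why IgG is scored below its own detection limit, and a count of censored results does not show what they do to the fold rises.

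A reader might infer three stronger things, none of which the documents support:
- **That fold rises are inflated as a matter of fact.** The size depends on an unstated share, and at a very high share with wide spread the quarter rule overstates the GMC instead.
- **That half-LLOQ is the correct rule.** Step 4 shows it can be the worse of the two.
- **That the cross-cohort fold-rise ratios are biased upwards.** They can move either way.

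**Conclusion.** The point holds as a minor one. The IgG value is a quarter of the LLOQ for all 13 serotypes, it differs from the OPA rule, and the SAP neither explains it nor plans a check. If ln concentrations are normal with SD 1.0, pre-vaccination or Hib-arm GMCs would be 9 to 25% too low, and fold rises and 13vPnC/Hib GMRs 10 to 34% too high, for censored shares from 10 to 50%. Half-LLOQ would be closer up to a share of about 30% across the tabulated SDs.

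These sizes rest on two assumptions that the documents cannot confirm: the censored share, and a log-normal spread before vaccination similar to that seen after it. With no censored samples there is no effect. The primary non-inferiority comparison and the proportions at or above 0.35 µg/mL are effectively unaffected.

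**What to change.** In SAP 5.3.1, keep the 0.5 × LOD results so that they stay comparable with the completed primary report, and state the reason for that value. Add an analysis of the IgG baseline GMCs, GMFRs, ratios of GMFRs and 13vPnC/Hib GMRs that fits a normal model on the ln scale with results below the LLOQ treated as left-censored. Apply it to serotypes and time points with an appreciable share below the LLOQ, for example above 10%, and report it beside the table in SAP 6.3.1.4. This model needs no choice of substitute value and has little bias when ln values are in fact normal. Report the 0.5 × LLOQ result as well, to match OPA.

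The cost is a short SAP addition and some extra programming, with no new data. Fold rises may look slightly less favourable.
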